6. PRIMARY ENDPOINT

The primary outcome measure will be the tolerability of the application of the stem cell recovery complex (SCR Complex™) and a botanical lipid based occlusive (Bio Cel™) as compared with standard of care following fractional RF treatments.

7. SECONDARY ENDPOINTS

The secondary outcomes will be the subject's degree of discomfort and/or pain as measured by the visual analogue scale (VAS), the incidence of spontaneous adverse events (AEs) and the investigator's assessment of improvement using the Fitzpatrick Wrinkle and Elastosis Scale scores before and after treatment as well as Global Aesthetic Improvement Scale (GAIS) for each subject.

8. RANDOMIZATION

Subjects will be randomized to receive either standard of care (SOC) treatment (no topical therapy for 24 hours post fractional RF treatment) or a topical adjuvant combination treatment utilizing SCR Complex™ and Bio Cel™. The order of treatment will be assigned to subjects through subject number. All subjects will resume skin care as per VenusSkin protocol 24 hours post fractional RF treatments.

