11.1 Screening Visit

The following procedures will be performed at the screening visit:

- Written informed consent
- Assign unique identifying number
- Inclusion/exclusion criteria
- Demographics
- Physical examination
- Medical history
- Concomitant medications
- Skin type (Fitzpatrick Scale)
- Wrinkle evaluation (Fitzpatrick Wrinkle and Elastosis Scale)
- Test spot

Test Spot

In order to assess tolerability to treatment, up to three test spots will be performed on the area adjacent to the ear on the side of the neck close to the back (so as it is not visible). Test spots should be based on skin type and desired outcome as per the chart below. The test spots will be used to determine the optimal parameters / setting combinations prior to the first treatment and later, the second treatment.

- Following the test spot, wait to ensure that the chosen parameters indeed lead to the appropriate immediate response.

- If slight erythema and edema and no adverse events occurred, treatment should be continued using the same setting or increase by not higher than ~10% parameters for each session.
- If no results are observed, the treatment parameters should be increased.
- If the patient has experienced adverse events along with improvement, the treatment parameters should be decreased.
- Fine-tuning of the parameters can be done before proceeding to treat the entire sub-area with the chosen parameters. Modification of parameters per treated area within a treatment session should only be carried out if required due to safety concerns.

Assessment of the test spot will be performed following at least 2 hours and up to 48 hours depending on skin type. As such, the first treatment may be conducted on the same day as screening. It is important to not start treatment prior to full evaluation of the reaction to the test spot and having optimal parameters identified.

Table 1 - Test spot and treatment parameter chart

Starting parameters			
Skin Type	Mild	Moderate	Intense
I-II	220v / 30ms	250v / 15ms	280v / 15ms
III-IV	220v / 15ms	240v / 15ms	240v / 30ms
V-VI	220v / 10ms	230v / 5ms	240v / 5ms

Test Spots Mild			
Skin Type	Mild spot 1	Mild spot 2	Mild spot 3
I-II	220v / 5ms	220v / 15ms	220v / 30ms
III-IV	220v / 5ms	220v / 10ms	220v / 15ms
V-VI	220v / 5ms	220v / 8ms	220v / 10ms

Test Spots Moderate			
Skin Type	Moderate spot 1	Moderate spot 2	Moderate spot 3
I-II	250v / 5ms	250v / 10ms	250v / 15ms
III-IV	240v / 5ms	240v / 10ms	240v / 15ms

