11.2 Treatment Visits

Subjects that did not experience significant pain or skin sensitivity in response to the test spots can receive treatments. Each subject will be enrolled and scheduled for two treatments, three weeks apart and return for a follow-up visit three days after the second treatment for evaluation of the treatment area.

The following procedures and assessments are required at the treatment visits:

Pre-treatment

- Confirm continued eligibility regarding inclusion/exclusion criteria
- Review any changes in medication, health status or AE from last visit
- Assessment of adverse events including a photograph of the affected treatment area if an adverse event occurred
- Assessment of concomitant medications
- Assign randomized treatment (after 1st treatment visit only)
- Apply a topical anesthetic preparation over the treatment areas, if required. (If used, record in the CRF.)

Treatment

No lotion, gel or coupling medium is to be used in this treatment. The distal part of the applicator should be clean and dry before fitting it with a new 160 pins tip. The skin in the treated area should also be cleaned well (for removal of any lotions, make-up residues, topical anesthetic cream, etc.) and patted dry. Hairs that exist in the areas should be shaved off.

- Treatment should be performed while the subject is lying down comfortably; the operator should have easy access to the subject's treatment area.
- Areas of dental crowns, caps, braces, or other metal dental implants may be more sensitive to treatment and the clinician may use dental rolls, gauze or a tongue depressor to isolate the area and make the treatment more comfortable (if the face is treated).
- Treatment of subjects in hair-bearing areas may result in some damage to the follicles and subsequent loss of hair. Avoid the beard area (if face is treated) and other hair growing zones if the patient doesn't wish to have reduction of the hair growth. This treatment may also result in in-grown hairs.
- The applicator should be held perpendicular to and in close contact with the skin.
- Pressing the trigger will release the RF energy to the skin, creating a stamped imprint in a shape and intensity depending on energies.

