- The immediate responses, indicative of the desired effect, are erythema and edema in the immediate area of the stamp and possibly also around it. The edema usually appears 1-2 minutes post-treatment and reaches its peak (of up to moderate edema) within 30 minutes. It should be noted that erythema is not easily noticeable, if at all, in darker skin types, so the edema will indicate a more significant effect in these subjects.
- Treatment consists of a single pass over the designated area.
- Unless otherwise instructed, the energy parameters can be modified between the treatment visits, as per the Investigator's discretion.
- It is recommended that throughout the study, that one staff member administer the treatments and another staff member perform the evaluations of the treatment area.

Post Fractional RF Treatment

- Subject Discomfort Assessment recorded on a 100mm visual analogue scale (VAS) immediately post treatment.
- Subject Tolerability Scale immediately post treatment.
- Subjects will receive either the adjuvant combination treatment (SCR Complex™ followed by Bio Cel™ occlusive gel applied to the treatment area) or SOC (no topical applications to treatment for 24 hours post fractional RF treatment).
- Subjects will be asked to complete the Subject Home Tolerability Scale at 24 hours and 72 hours post-treatment
- Subjects will be provided with the Subject Home Instruction Sheet (Appendix B).
- A follow-up telephone call will be made to the subject 24 and 72 hours after the first treatment and 24 hours after the second treatment. Study staff will ask the subject to report on the treatment using the Self-Report Adverse Event Questionnaire (Appendix C) and remind the subject to complete and return to the clinic with their completed Subject Home Tolerability Scale at each visit.

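### No allocation concealment is described, and Section 11.2 contradicts itself on when the treatment arm is assigned

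*Combined protocol and SAP*

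**What the plan says.** Section 8 randomizes each subject to standard of care (SOC, no topical for 24 hours) or to SCR Complex plus Bio Cel. Its only statement of mechanism is "The order of treatment will be assigned to subjects through subject number". No ratio, sequence generation, list holder or concealment step appears there or elsewhere in the text available for review, from which a few pages were removed.

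The one number visibly issued is at screening, where Section 11.1 has the item "Assign unique identifying number".

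Section 11.2 has a pre-treatment list of six items. The first is "Confirm continued eligibility regarding inclusion/exclusion criteria", the fifth is "Assign randomized treatment (after 1st treatment visit only" (the words in brackets close there), and the sixth is "Apply a topical anesthetic preparation over the treatment areas, if required". Its list for the period after the RF pass also has six items: the VAS first, "Subject Tolerability Scale immediately post treatment" second, and the topical or SOC third.

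The Schedule of Events (Section 1) has no row for randomization. Section 14 includes the immediate rating in the primary tolerability summary and compares VAS between the groups.

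**The concern.** The trial is open-label and its primary outcome is the subject's own rating. Blinding gives no protection, so the plan relies on randomization being concealed until it is needed and released at a defined moment. Neither is written down.

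Timing matters most at the first treatment visit. If the arm is released before the RF pass, staff know it when they decide on anaesthetic and when they handle the subject. The subject may know it too, since the plan does not say when subjects are told. Suppose the immediate tolerability rating and the VAS are taken before any topical is applied. A difference between arms on them at that visit could not then be an effect of the topical. With the arm already known, expectation or handling could produce such a difference; with the arm still hidden, they could not act differently by arm.

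The two centres could also follow the same text in different ways.

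**Working it through.** The plan gives no figure for this point, so the check compares passages and makes a simple count.

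**Concealment.** Section 8 ties the arm to a number. Section 11.1 issues a number at screening. That these are the same number is an inference, and even then the number could index a hidden list. The supported finding is that concealment is not described.

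**Time of assignment.** Three readings of the Section 11.2 item are possible:

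| Reading | Fits the pre-treatment heading? | Fits giving the topical or SOC at the same visit? | Consequence |
|---|---|---|---|
| After the first visit has ended (literal) | No | No | Cannot be carried out |
| Before the RF pass (by heading) | Yes | Yes | Arm can be known before the anaesthetic decision, the RF pass, VAS and immediate rating |
| After the first RF pass, within the visit | No | Yes | Workable, but the item is in the wrong list |

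No reading satisfies the heading, the words in brackets in their literal sense and the topical step together. The Schedule of Events does not settle it.

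**Ratings affected on the heading reading.** Inputs are Sections 1, 11.2 and 11.3, counting the 72-hour rating after the second treatment once, at follow-up.

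- Tolerability per subject: first treatment at 0, 24 and 72 h = 3; second treatment at 0 and 24 h = 2; follow-up at 72 h = 1. Total 3 + 2 + 1 = 6.
- VAS per subject: one at each treatment visit = 2.
- Listed before the topical at the first visit: 1 of 6 tolerability ratings (17%) and 1 of 2 VAS ratings (50%).
- With up to 100 evaluable subjects: up to 100 of 600 tolerability ratings and up to 100 of 200 VAS ratings.

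The remaining 5 tolerability ratings and 1 VAS rating per subject follow the first application of topical or SOC, so they are open-label whichever reading is used. These are counts of exposed ratings. They do not measure bias, and the documents give nothing from which bias could be estimated.

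**RF settings.** Section 11.1 states: "It is important to not start treatment prior to full evaluation of the reaction to the test spot and having optimal parameters identified". It also allows that "Fine-tuning of the parameters can be done before proceeding to treat the entire sub-area with the chosen parameters", but the next sentence there confines changes within a session to safety concerns. The choice of settings therefore normally comes before assignment, and the route from a known arm to different RF handling at the first visit is small.

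**The case against.** The strongest objection is that list order is not time order. The list after the RF pass names the 24- and 72-hour home ratings before the handing over of the instruction sheet. The Schedule of Events puts eligibility above consent, while Section 11.1 lists consent first. This stands: a pre-topical immediate rating is likely from the list but not established, so the count above is conditional. The contradiction between the heading and the words in brackets does not depend on list order.

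It can also be said that the timing item is only misplaced, since one reading is workable. That may be so, but the text does not say which reading is meant.

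Several stronger conclusions are tempting and are not supported:

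- *Allocation is predictable.* No rule such as odd or even numbers is stated, and the number may point to a concealed list. Section 13 has separate screening and enrolment logs, and Appendix C uses a patient number within a site code, so a number issued at enrolment is also plausible.
- *Entry to the trial is biased.* Section 11.2 lists confirmation of eligibility before assignment. Entry bias would need a screening number that reveals the arm.
- *A quarter of the self-ratings are compromised.* Adding the two scales gives 2 of 8, but this pools primary and secondary outcomes and counts exposure only.
- *The design is a crossover.* The word order in Section 8 is awkward for one arm per subject, but it can mean the allocation sequence. The rest of the plan describes parallel groups.

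**Conclusion.** The point holds in a limited form and should be fixed. Two things are established: no concealment is described in the text available, and the stated time of assignment is either unworkable or, by its heading, earlier than it need be. Missing concealment alone would be close to a missing detail. Together with a timing rule that cannot be followed as written, it becomes a design matter for which a better and cheap rule exists.

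The exposure is confined to the first treatment visit: the anaesthetic decision, a small RF-handling route, one tolerability rating and one VAS rating per subject. This rests on the heading reading and, for the two ratings, on list order reflecting time order. The size of any bias is unknown. Concealed late release would not protect later ratings, which remain open-label.

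**What to change.** 1. In Section 8, specify a pre-generated allocation list with concealed release, either central or by sequentially numbered sealed opaque envelopes, that cannot be read from the screening number. Refer to the treatment arm in place of an order of treatments.
2. State one release moment at the first treatment visit: after eligibility, any anaesthetic, the RF pass, the VAS and the immediate tolerability rating have been recorded, and immediately before the topical or SOC step.
3. Add that moment to the Schedule of Events and reconcile Sections 8, 11.1, 11.2 and 14 with it.

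Three downsides should be stated in the plan:

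- The first-visit VAS and immediate tolerability rating become pre-topical by rule. They then serve as pre-intervention values and not as measures of the adjuvant, so the Section 14 account of the primary summary and the VAS comparison must say so.
- A subject who stops during the first RF pass has no arm. Section 14 includes everyone who received any treatment, so it must say that such subjects are reported separately.
- One step is added at the first treatment visit, between the ratings and the topical.

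Undisclosed varied block sizes, if blocks are used, and reporting of RF settings by arm are optional. The cost is an allocation list, envelopes or a central release, and protocol wording. No extra visits or subjects are needed.

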9. SUBJECT SELECTION AND WITHDRAWAL

Inclusion Criteria

Subjects must satisfy the following criteria to be enrolled in the study:

1. Male or non-pregnant, non-nursing female at least 21 years of age and less than 75 years of age.
2. Undergoing a dermatological procedure requiring ablation and resurfacing of the facial skin utilizing the Venus Viva™ SR system.

3. Women of child-bearing age are required to be using a reliable method of birth control prior to enrollment and throughout their participation in the study.
4. Able to tolerate the treatment as determined by a test spot application(s).
5. Mentally and physically competent to sign an informed consent document indicating that they understand the purpose and procedures required for the study and are willing to participate.
6. Able and willing to comply with the treatment/follow-up schedule

Exclusion Criteria

Subjects who meet any of the following criteria will be excluded from participation in the study:

1. Superficial metal or other implants in the treatment area.
2. Tattoos, permanent makeup, scars or piercings in the treatment area.
3. Current or past history of significant systemic illness.
4. Any active condition in the treatment area, such as sores, psoriasis, eczema and rash.
5. Subjects with a pacemaker or planned cardioversion in the future.
6. Receiving therapies or medication that may interfere with the study treatment.
7. Any surgical procedure in the treatment area within the last three months or before complete healing.
8. Currently receiving or received within 6 months before the planned start of treatment, an investigational drug / experimental medical device.
9. Any physical or mental condition, as per the investigator's discretion, which may make it unsafe for the subject to participate in this study.

Subject Withdrawal Criteria:

A subject has the right to withdraw from the study at any time, for any reason, without prejudice to her future medical care by the physician or the institution. Should a subject (or the subject's legally authorized representative) decide to withdraw, all efforts will be made to collect and report the final visit observations as thoroughly and timely as possible. Permission to contact subjects for the purpose of determining their status even after participation in the study is complete will not require additional ethics approval.

Subjects may be removed from the study if any one or more of the following events occur:

- Refusal of the subject to continue treatment and/or observations
- Decision by the Investigator that termination is in the subject's best medical interest
- Device failure
- Subject is lost to follow-up
- Other ethical or clinical considerations

Subjects will be recruited through chart review from the investigator sites, referrals or any type of media advertising. All screened subjects will be recorded on a screening log. Any information given to subjects and any advertisements intended for use for this study must be approved by the site's ethics board prior to use.

10. DEVICE and INVESTIGATIONAL PRODUCTS

10.1 Venus Viva™ System

The Venus Viva™ system is a fractional RF system that is intended for dermatological procedures requiring ablation and resurfacing of the skin. The Venus Viva™ device is a non-significant risk device. Consistent with 21 CFR 812.66, the device does NOT meet the criteria for significant risk device:

- It is not an implant and does not present a potentially serious risk.
- The device does not support or sustain human life, or present a potential for serious risk.
- The device is not used for a substantial importance in: diagnosing, curing, mitigating, or treating disease, or preventing impairment of health. The investigational device could not cause significant harm to any of the subjects.

The device could not cause any of the following potential harmful situations.

- Life threatening
- Permanent damage to body function
- Permanent damage to body structure
- Necessitate medical or surgical intervention
- Preclude permanent impairment of a body function
- Preclude permanent damage to body structure

The device does not appear on the FDA significant risk device list.

Maintenance

The part of the system that touches the subject's body (applied PINS) is disinfected prior to each treatment using a brush and disinfectant provided by Venus Concept®. The applicator is allowed to dry off completely between each use.

10.2 Topical Study Treatments

SCR Complex™ contains human growth factors and cytokines derived through laboratory culture of human bone marrow mesenchymal stem cells. Science recognizes these cells as "commander in chief" of healing in all tissues. These are migratory cells that "patrol" all tissues via the blood stream. In culture they produce patterns of growth factors and cytokines that are pro-healing and anti-inflammatory. Their numbers plummet with age so that by age 50 only 4% of the relative number at birth remains. Additional recombinant technology derived growth factors help promote fetus-like, non-fibrotic, anti-inflammatory healing.

Topical application of these bio-signals in conjunction with fractional laser resurfacing and dermal needling has resulted in enhanced healing and aesthetic improvements when combined with dermal needling.

Bio Cel™ is a botanical lipid-based gel occlusive that provides effective reduction in trans-dermal water loss and environmental contamination following ablative and semi-ablative procedures. Other

ingredients include a patented lipid soluble form of boric acid (provides bacteriostatic, anti-inflammatory and analgesic properties), tocopheryl acetate, and TGF-beta 3, a powerful anti-inflammatory growth factor.

Packaging

Topical study treatments (**SCR Complex** and **Bio Cel Occlusive**) will be provided to the study sites as commercially available product labeled for use in clinical trials only. In accordance with laws and regulations, the label will include the trade name, name and address of the manufacturer, quantity of contents, batch code and all other essential information.

Receipt, Storage, and Destruction

Topical study treatments will be shipped to the site from a central facility.

At the site, the topical study treatments will be stored at room temperature.

At the completion of the study, the topical study treatments will be destroyed as per the site's normal standard of practice for topical treatments.

11 STUDY PROCEDURES

Section 1, Schedule of Events, summarizes the type and frequency of each study procedure to be performed in this study.

11.1 Screening Visit

The following procedures will be performed at the screening visit:

- Written informed consent
- Assign unique identifying number
- Inclusion/exclusion criteria
- Demographics
- Physical examination
- Medical history
- Concomitant medications
- Skin type (Fitzpatrick Scale)
- Wrinkle evaluation (Fitzpatrick Wrinkle and Elastosis Scale)
- Test spot

Test Spot

In order to assess tolerability to treatment, up to three test spots will be performed on the area adjacent to the ear on the side of the neck close to the back (so as it is not visible). Test spots should be based on skin type and desired outcome as per the chart below. The test spots will be used to determine the optimal parameters / setting combinations prior to the first treatment and later, the second treatment.

- Following the test spot, wait to ensure that the chosen parameters indeed lead to the appropriate immediate response.

- If slight erythema and edema and no adverse events occurred, treatment should be continued using the same setting or increase by not higher than ~10% parameters for each session.
- If no results are observed, the treatment parameters should be increased.
- If the patient has experienced adverse events along with improvement, the treatment parameters should be decreased.
- Fine-tuning of the parameters can be done before proceeding to treat the entire sub-area with the chosen parameters. Modification of parameters per treated area within a treatment session should only be carried out if required due to safety concerns.

Assessment of the test spot will be performed following at least 2 hours and up to 48 hours depending on skin type. As such, the first treatment may be conducted on the same day as screening. It is important to not start treatment prior to full evaluation of the reaction to the test spot and having optimal parameters identified.

Table 1 - Test spot and treatment parameter chart

Starting parameters			
Skin Type	Mild	Moderate	Intense
I-II	220v / 30ms	250v / 15ms	280v / 15ms
III-IV	220v / 15ms	240v / 15ms	240v / 30ms
V-VI	220v / 10ms	230v / 5ms	240v / 5ms

Test Spots Mild			
Skin Type	Mild spot 1	Mild spot 2	Mild spot 3
I-II	220v / 5ms	220v / 15ms	220v / 30ms
III-IV	220v / 5ms	220v / 10ms	220v / 15ms
V-VI	220v / 5ms	220v / 8ms	220v / 10ms

Test Spots Moderate			
Skin Type	Moderate spot 1	Moderate spot 2	Moderate spot 3
I-II	250v / 5ms	250v / 10ms	250v / 15ms
III-IV	240v / 5ms	240v / 10ms	240v / 15ms
V-VI	225v / 5ms	225v / 10ms	230v / 5ms

Test Spots Intense			
Skin Type	Intense spot 1	Intense spot 2	Intense spot 3
I-II	270v / 5ms	280v / 5ms	280v / 15ms
III-IV	240v / 5ms	240v / 15ms	240v / 30ms
V-VI	230v / 5ms	235v / 5ms	240v / 5ms

It is recommended to perform three test spots on the area adjacent to the ear on the side of the neck close to the back (so it is not visible). Test spots should be based on skin type and desired outcome as per the chart above. A test spot should be performed at the energy settings recommended in the chart above.

It is recommended that each subsequent treatment you increase the total % of energy no higher than 10% for each session.

